4 OBJECTIVES AND ENDPOINTS

OBJECTIVES	ENDPOINTS
Primary	
To determine the extent to which clinician notification with nurse facilitation (CNNF) versus usual care is associated with differences in the proportion of patients who have medication optimization (defined as either discontinuation of all antiplatelet drugs or initiation and adherence to a PPI based on self-report) at week 7-10.	The proportion of patients who self-report either discontinuing all antiplatelet therapy (defined as none in the past 7 days) or initiating and adhering to a proton pump inhibitor (defined as use for at least 5 of the prior 7 days) at week 7-10.
Secondary	

To determine the extent to which CNNF (vs usual care) is associated with differences in the proportion of patients who are recommended to have medication optimization based on chart review after 6 weeks.	The proportion of patients with a documented recommendation in the electronic health record to either discontinue all antiplatelet therapy or initiate a PPI
Exploratory	
To determine how often the anticoagulation clinic nurse communicated the recommendation to either discontinue all antiplatelet therapy or start a PPI for patients who were randomized to receive CNNF.	The proportion of patients for whom an anticoagulation clinic RN documented communicating a recommendation to the patient to either discontinue all antiplatelet therapy or start a PPI based on chart review.
To determine how often the anticoagulation clinic nurse pended an order for a PPI for patients randomized to CNNF and recommended by their clinician to initiate PPI.	The proportion of patients for whom an anticoagulation clinic RN pended an order for a PPI among patients randomized to CNNF and recommended by their clinician to initiate PPI.
To explore why patients recommended to either discontinue an antiplatelet drug or initiate a PPI may choose not to make the medication change.	The reasons why patients who received a recommendation to make a medication change chose not to adhere to the recommendation according to patient self-report at week 7-10 (qualitative).

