To explore the accuracy of the electronic health record's medication list for PPIs and antiplatelet drugs at baseline.	
The proportion of patients who, retrospectively, report that they had been using antiplatelet therapy at baseline during the patient phone survey at week 7-10.
 
The proportion of randomized patients who, retrospectively, report that they had been using PPI at baseline during the patient phone survey at week 7-10.

To explore the accuracy of the electronic health record's medication list for PPIs and antiplatelet drugs at week 7-10.	
The accuracy of the EHR medication list at week 7-10 for antiplatelet drugs compared to self-report.
 
The accuracy of the EHR medication list at week 7-10 for proton pump inhibitors compared to self-report.

To explore the appropriateness of antiplatelet therapy used by patients at the time of study entry.	The clinical appropriateness of baseline antiplatelet therapy as determined by a physician reviewing the medical record. Antiplatelet appropriateness will be categorized as probably guideline concordant, probably not guideline concordant, or uncertain in reference to

	practice recommendations (Appendix 1). Baseline antiplatelet therapy will be ascertained by self-report at week 7-10.
To explore the extent to which CNNF (vs. usual care) is associated with the appropriateness of antiplatelet therapy at week 7-10.	
The clinical appropriateness of antiplatelet therapy at week 7-10 (relative to appropriateness assessment at the time of study entry, as determined by a physician reviewing the medical record). Antiplatelet appropriateness will be categorized as probably guideline concordant, probably not guideline concordant, or uncertain in reference to practice recommendations (Appendix 1). Antiplatelet therapy at week 7-10 will be determined by patient self-report.
 
We will also evaluate this endpoint for the subset of patients who were recommended to make a medication change.

To explore fidelity to the CNNF vs. usual care	
Fidelity to CNNF will be determined by performing a chart review on patients whose clinicians received the CNNF strategy, to confirm that it was delivered as intended.
 
We will also perform chart review for patients randomized to usual care to ensure that they did not receive CNNF.

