8.3 Lost to Follow-Up

For patients unable to be reached for the phone survey at week 7-10, chart review will still be performed.

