11 STATISTICAL CONSIDERATIONS

11.1 Sample Size Determination

The study is powered to have 90% power to identify a difference between usual care and CNNF with a two-sided 5% type I error. We estimate that the rate of medication optimization will be 5% with usual care and 35% with CNNF. In the pilot study, we observed substantial variation at the clinician-level in whether clinicians responded to the notification messages at all. In our sample size estimates, we therefore assumed a high-level of correlation in the outcome for patients within clinician clusters (ICC=0.95). While our clinician population includes providers with 1-32 patients, if a clinician is selected to participate who has more than 4 patients (27/156), we will

randomly select 4 of their patients to participate in order to avoid overwhelming some clinicians with a large number of notifications in a short period of time. Therefore, capping the 27 providers who have more than 4 participants, there is a coefficient of variation=0.62 (calculated using preliminary data) of the number of patients per provider and an average of 2 participants per clinician. For 90% power to detect the 30% difference between interventions, we require 44 clinicians/arm and 176 total patient participants. We will assume a 20% dropout or ineligibility rate, so we plan to increase the N (176/0.8). This results in a final N of 220, equating to 110 participants and 55 clinicians per arm.

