11.5 Analysis of the Primary Endpoint(s)

We will use generalized linear mixed effects modeling (logit link) to estimate the odds of medication optimization at week 7-10. This model will include fixed effects for CNNF (vs. usual care), target provider specialty and size, and a random effect for clinician to account for the clustering of patients. We will report the odds ratios with corresponding confidence intervals for the main effect. The main effect will be tested at a two-sided 5% significance level. Sensitivity analyses will adjust for patient age, gender, comorbidities, antiplatelet drug at study entry, and clustering at the nurse level.

For patients who were unable to be contacted by phone for the week 7-10 phone call (lost to follow up), or who declined to participate, we will perform exploratory analyses to determine whether they differed (with respect to demographic characteristics, medical history, or target clinician specialty) from patients who were able to be reached. We will use multiple imputation to account for any missing data for the patients lost to follow up considering all demographic, medical history and target clinician specialty variables considering the data missing at random and combine results across imputation via Rubin's rules. Best and worst case sensitivity

analyses will assess the robustness of the findings and provide the range of uncertainty of conclusions made. For patients who call back the research team after week 10, the survey will still be completed, but their outcome will be considered missing and imputed in primary analysis with a sensitivity analysis using the week 10 outcome.

Patients who reported at the week 7-10 phone call that they were either not using antiplatelet therapy at the start of the trial or were using a PPI will be included in the primary ITT analysis. We expect those who were not initially eligible to be balanced across the groups, thus the comparison of CNNF vs usual care will remain valid; however, for more accurate estimates, we will also conduct a per-protocol analysis where we exclude these individuals.

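### The imputation of missing primary outcomes names only baseline variables, although week 7-10 chart data on the same unreached patients could be used as auxiliary variables

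*Combined protocol and SAP*

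**What the plan says.** Section 11.5 treats the primary outcome as missing for patients who cannot be contacted, who decline, or who call back after week 10. For patients lost to follow-up it plans multiple imputation, "considering all demographic, medical history and target clinician specialty variables considering the data missing at random", combined by Rubin's rules. The comparison of reached with unreached patients uses the same three groups of variables. Best and worst case analyses, and one that uses the late call-backs, are planned as sensitivity analyses.

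Elsewhere the protocol keeps collecting data on the same patients. Section 8.3 states: "For patients unable to be reached for the phone survey at week 7-10, chart review will still be performed". Section 8.1 says the same of patients who are not phoned because they stopped warfarin or left the service after delivery. Section 4 shows what chart review yields. The secondary endpoint is "The proportion of patients with a documented recommendation in the electronic health record to either discontinue all antiplatelet therapy or initiate a PPI". One exploratory endpoint is "The accuracy of the EHR medication list at week 7-10 for antiplatelet drugs compared to self-report", and there is a matching one for PPIs. Section 11.5 mentions none of this for the imputation.

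**The concern.** The outcome is a medication change made after entry. Age, history and clinician specialty cannot separate an unreached patient who stopped aspirin or started a PPI from one who did neither. A documented recommendation is a step on the path to the outcome, and the medication list in the same window is a direct, if imperfect, record of it.

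Missing at random is harder to defend when only baseline traits are conditioned on. In the CNNF arm the nurse may communicate the recommendation to the patient, and the outcome is collected by telephone. A patient who is hard to reach could miss both, and one who did not follow advice could avoid the call. Some missing outcomes are to be expected: 9.2 allows three call attempts without remuneration, and 6.6 plans no retention measures. What is at stake is the size of the primary effect estimate, and how far its missing-data assumption can be defended.

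**Working it through.** **Inputs from section 11.1.** Power and error: "The study is powered to have 90% power to identify a difference between usual care and CNNF with a two-sided 5% type I error". Rates: "We estimate that the rate of medication optimization will be 5% with usual care and 35% with CNNF". ICC 0.95, mean cluster size 2, and "there is a coefficient of variation=0.62". Dropout or ineligibility is 20%, used here as the missing-outcome fraction (an assumption, because the plan's 20% also covers ineligibility).

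**The plan's own figure.**
- Variance term: 0.05×0.95 + 0.35×0.65 = 0.275.
- Unclustered n per arm: (1.960 + 1.282)² × 0.275 / 0.30² = 32.11.
- Design effect: 1 + [(1 + 0.62²)×2 − 1]×0.95 = 2.680.
- Patients per arm: 32.11 × 2.680 = 86.06, which is 43.03 clinicians, rounded up to 44. Total 176, and 176/0.8 = 220. The plan's figures reproduce.

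**Bias, illustration A: response depends on the outcome in the CNNF arm.** The documents give no response pattern, so these rates are assumed: 90% of optimized and 75% of non-optimized CNNF patients respond, and 80% of usual-care patients respond whatever their outcome.
- CNNF response: 0.35×0.90 + 0.65×0.75 = 0.8025, so about 20% are missing.
- Imputation by arm without chart data: 0.315/0.8025 = 39.3%. Difference 39.3 − 5.0 = 34.3 points; marginal odds ratio 12.3, against a true 30.0 and 10.2.
- Add a chart proxy with assumed sensitivity 80% and specificity 95%. Proxy-positive patients are 0.28 + 0.0325 = 0.3125 of the arm, and the rate among their respondents is 0.252/0.2764 = 91.2%. Proxy-negative patients are 0.07 + 0.6175 = 0.6875, and the rate is 0.063/0.5261 = 12.0%. Estimate: 0.3125×0.912 + 0.6875×0.120 = 36.7%. Difference 31.7 points; marginal odds ratio 11.0.
- The same steps give 31.0 points at 90%/97% and 32.6 points at 70%/90%.

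**Bias, illustration B: response depends on the recommendation in the CNNF arm.** Assume that 50% have a documented recommendation, of whom 70% are optimized, and that none of the others are (0.5×0.7 = 0.35).
- Missing 10% with and 30% without a recommendation: 0.5×0.9×0.7/0.8 = 39.4%, difference 34.4 points.
- Missing 26.7% with and 13.3% without: 0.5×0.733×0.7/0.8 = 32.1%, difference 27.1 points.
- Equal missingness: difference 30.0 points, no bias.
- Imputing within recommendation status returns 0.5×0.7 + 0.5×0 = 35% in every case.

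The sign can therefore go either way, and the bias is zero if reachability is unrelated to the chart variable within arm.

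**Precision, with clustering.** Standard error of the simple difference in proportions, with 110 patients per arm:
- Full data: √(0.275×2.680/110) = 8.2 points.
- 20% missing completely at random: clusters also shrink, so the design effect falls to 1 + 0.8×1.680 = 2.344, and √(0.275×2.344/88) = 8.6 points.
- The variance rises by about 9%, and even a perfect proxy could recover only about 0.4 points. Simulation with beta-binomial clusters (20,000 runs, coefficient of variation about 0.59) gives 8.0 and 8.4.

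**Best and worst case bounds** at 20% missing per arm. The observed optimized fractions are 0.35×0.8 = 0.28 and 0.05×0.8 = 0.04. Worst: 0.28 − (0.04 + 0.20) = +4 points. Best: (0.28 + 0.20) − 0.04 = +44 points.

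**The case against.** A reader might infer that bias is present in the primary result. The documents do not support that. Nothing in them shows that reachability depends on outcome or chart status, and the figures above rest on assumed response rates.

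A reader might also infer a real loss of precision or power. Treating patients as independent, √(0.275/110) = 5.0 and √(0.275/88) = 5.6 points, which looks like a 25% rise in variance. At ICC 0.95 that does not describe this trial: cluster-mates carry most of the missing information, and the rise is about 9%. The increase from 176 to 220 already allows for dropout, so the 90% power target does not depend on this change.

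Third, the remedy does not cure illustration A. Response there depends on the outcome itself, so 1.0 to 2.6 points of bias remain, and the accuracy of the medication list is itself an open question in section 4.

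Fourth, 11.5 does not say that only the listed variables may be used: chart variables are unnamed, not excluded. Nor is it certain that the list is abstracted for unreached patients, because that endpoint is defined against self-report, which they lack.

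These points stand as limits on size and certainty. The planned best and worst case analyses are a genuine safeguard, but a range of +4 to +44 points displays the uncertainty without improving the primary estimate. None of this argues for conditioning on baseline traits alone when better information is at hand.

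**Conclusion.** The point holds as an inexpensive improvement to the primary analysis, not as a demonstrated error. The imputation variables that 11.5 names are weak predictors of a post-entry change, and the protocol keeps chart review from the same window for patients who lack the phone outcome. Under the assumed patterns, imputation without chart data could move a 30-point difference by roughly −3 to +4 points. Chart variables would remove that bias if the outcome is missing at random given them, and would only reduce it (34.3 to between 31.0 and 32.6 points) if missingness depends on the outcome itself. The gain in precision is too small to be a reason for the change.

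These results rest on the planning rates, about 20% missing, and assumed response rates and chart accuracy. They are large-sample marginal differences and odds ratios, not the clinician-conditional odds ratio that the mixed model will report.

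**What to change.** In 11.5, name as auxiliary variables in the imputation model, alongside arm and clinician:
1. documented recommendation, yes/no;
2. week 7-10 MiChart status, antiplatelet listed yes/no and PPI listed yes/no.

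Read the medication list at a fixed index date that applies to every patient and falls before any reconciliation prompted by the study call. Section 9.2 lets the call trigger chart correction, which can happen only in reached patients, so a later reading would be more accurate in them than in those being imputed. A rule tied to the call itself would not work, because unreached patients have no completed call. Confirm that the list is abstracted for unreached patients, and say whether patients not phoned under 8.1 are imputed as lost to follow-up.

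Keep these variables out of the analysis model, since they are measured after randomization and lie on the path to the outcome. Add them, by arm, to the planned comparison of reached and unreached patients.

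Cost: a short addition to 11.5, a dating rule, and a little more abstraction, with no new patient contact. With about 5 expected usual-care events (110×0.05 = 5.5, or 88×0.05 = 4.4 observed), the imputation model should be kept simple or penalized to avoid separation.

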11.6 Analysis of the Secondary Endpoint(s)

The approach for analyzing the secondary endpoints will be similar to the approach for the primary endpoint, using mixed effects modelling with a random effect for clinician.

11.7 Exploratory Analyses

Exploratory analyses will mainly consist of descriptive analyses using cross-tabulations, means, standard deviations and proportions, as well as regressions using a similar approach as for the primary outcome.

11.8 Other Analyses

N/A

11.9 Safety Analyses

N/A

11.10 Planned Interim Analyses

None planned.

11.11 Subgroup Analyses

N/A

12 SUPPORTING DOCUMENTATION AND OPERATIONAL CONSIDERATIONS

12.1 Regulatory, Ethical, and Study Oversight Considerations

12.1.1 Informed Consent Process

12.1.1.1 Quality improvement strategy delivery

The type of quality improvement strategy (clinician notification) described in this document is routinely used by the anticoagulation clinic as part of clinical care to improve the safety of patients using warfarin. The quality improvement strategy used in this pilot trial was developed specifically for use as part of a quality improvement effort to promote the use of evidence-based practices and reduce bleeding risk among the anticoagulation clinic's patient population.

We request a waiver of informed consent for delivery of the clinician notifications. This is justified on the grounds that the study presents only minimal risk to participants (and is likely to be beneficial), the waiver does not adversely affect the rights and welfare of participants, and the research could not practically be carried out without the waiver. The study could not practically be carried out if patients and clinicians are consented because the goals of this pragmatic quality improvement trial are to evaluate the effectiveness of these strategies when used as part of routine care for improving patient safety in the setting of upper GI bleeding risk reduction. The ethicality of this approach is further bolstered by the wait-listed control design, which will ensure that all participants will eventually receive the quality improvement strategies.

12.1.1.2 Patient phone survey

We request a waiver of informed consent for the conduct of the patient phone survey. The patient phone survey will consist of a one-time phone questionnaire anticipated to take 5 minutes (based on the duration of these calls in the pilot study). The survey will solely include questions that will allow the anticoagulation clinic to ensure that information in MiChart related to medications that influence bleeding risk are accurately documented in the patient's EHR both at baseline and at the time of the call and assess whether the patient made any medication changes during the study period. Accurate patient medication information in MiChart is necessary to correctly identify patients at high-risk for adverse events associated with warfarin use and knowledge of whether medication changes were made because of the study QI strategies or routine standard care is essential in assessing the impact of the strategy being tested and observing how often medication optimization occurs without CNNF, and as such these phone surveys are in-line with quality improvement efforts.

12.1.1.7 Chart Review for Randomized Participants

A waiver of informed consent will be sought for the chart review component of this study as it poses minimal risk to participants, does not adversely affect the risks and benefits of participation for the participant, and the study could not practically be completed without a waiver.

12.2 Confidentiality and Privacy

12.2.1 Future Use of Stored Specimens and Data

The data from this study may be used for future studies by the investigator team.

12.2.2 Data sharing

This study will be conducted in accordance with the National Institutes of Health (NIH) Public Access Policy, which ensures that the public has access to the published results of NIH funded research. It requires scientists to submit final peer-reviewed journal manuscripts that arise from NIH funds to the digital archive PubMed Central upon acceptance for publication. This study will also comply with the NIH Data Sharing Policy and Policy on the Dissemination of NIH-Funded Clinical Trial Information and the Clinical Trials Registration and Results Information Submission rule. As such, this trial will be registered at ClinicalTrials.gov, and results information from this trial will be submitted to ClinicalTrials.gov. In addition, every attempt will be made to publish results in peer-reviewed journals. Data from this study may be requested 3 years after the completion of the primary endpoint by contacting [name].

12.3 Safety Oversight

This study will not have a Data and Safety Monitoring Board or Safety Monitoring committee since it constitutes quality improvement.

12.5 Clinical Monitoring

N/A

12.6 Data Handling and Record Keeping

The source materials will include documentation of information collected during phone surveys and the results of chart review. Each study subject will be given a unique numeric identifier upon study entry. All individuals who wish to access the information system will need to pass through two levels of username and password authentication. All data will be stored on secured, password-protected UM computers. To access these data, approval must be obtained from the PI. These data will be kept only if specific use requires and then will be destroyed when all necessary linkages between data collection instruments have been accomplished.

Any paper records associated with this study will be stored at [name] in a locked cabinet.

12.7 Data Collection and Management Responsibilities

Data collection will be the responsibility of the research staff at the site under supervision of the PI. The PI will be responsible for ensuring the accuracy, completeness, legibility, and timeliness of the data reported.

All source documents will be completed in a neat, legible manner or collected in digital form to ensure accurate interpretation of the data.

12.8 Study Records Retention

As this trial will involve collection of health-related data through interaction with participants, all study documents will be retained for at least 7 years after the trial is completed in accordance with the University of Michigan's Human Research Protections Program (HRPP) Operations Manual Part 6.II.B.

